#### Calculation of the optimal contrasts

The optimal contrasts for each model depend on the dose spacing and hence can only be determined when the high dose (Part B) has been selected. The optimal contrasts will be calculated using the Dose Finding R-package (See [APPENDIX 2](#)). In this code, the low dose is expressed relative to the high dose. At the time of

---

execution, the scalar “dose.rat” will be replaced by ratio of the low dose over the high dose (R code in Appendix)

### **Multiple Contrast Test**

The MCT will be executed using the MCTtest-function of the R-package DoseFinding (version 0.9-16) using the R code (See **APPENDIX 2**). In this code, the low dose is expressed relative to the high dose. At the time of execution, the scalar “dose.rat” will be replaced by ratio of the low dose over the high dose.

#### Input:

1. mean.placebo = mean Week 24 HBsAg change from baseline in the placebo-group (arms pooled over Part A and Part B).
2. mean.low.dose = mean Week 24 HBsAg change from baseline in the JNJ379+NA group of |Part A
3. mean.high.dose = mean Week 24 HBsAg change from baseline in the JNJ379+NA group of |Part B
4. se.mean.placebo = standard error of the mean Week 24 HBsAg change from baseline in the placebo-group (arms pooled over Part A and Part B)
5. se.low.dose = standard error of the mean Week 24 HBsAg change from baseline in the JNJ379+NA group of Part A
6. se.high.dose = standard error of the mean Week 24 HBsAg change from baseline in the JNJ379+NA group of Part B

## **5.5. Exploratory Endpoints**

### **5.2.1 Parameters Definition**

The key exploratory endpoints for this study are

- Changes in the severity of liver disease.
  - Changes in fibrosis at week 24 (according to Fibroscan liver stiffness measurements) at end-of-treatment (EOT) and end of follow-up versus baseline will be analyzed.
- Explore HBV RNA and HBcrAg levels during study treatment and follow-up.

---

- Changes from baseline in HBV RNA and HBcrAg levels during study treatment and follow-up will be calculated
- Impact of viral and host baseline factors on different efficacy and safety parameters

### **5.2.1 Analysis Methods**

For continuous variables defined above, descriptive statistics (n, mean, SE, 95%CI, median, minimum, maximum) will be calculated; mean difference and CIs may be calculated where appropriate and a general linear mixed model will be used to compare the different study treatments. For categorical variables, frequency tables will be presented. Difference in proportions and 95%CIs may be calculated using a chi-square test of equal proportions where appropriate

In addition, changes from baseline to assess the severity of liver disease (changes in fibrosis according to Fibroscan liver stiffness measurements) at end-of-treatment (EOT) and end of follow-up versus baseline will be analyzed using a ANCOVA with treatment group, subject population (ie, subjects currently not being treated or virologically suppressed by current NA treatment), HBeAg status (positive/negative) as main effect in the model and baseline as covariate.

## **6. SAFETY EVALUATIONS**

All safety analyses will be performed using the Safety population. All assessments will be analyzed as described in section 2.6. Additionally, the displays will also be presented by analysis phase, analysis period and follow-up type except for the adverse event displays which will be displayed by analysis phase and follow-up type. The planned time points will be considered for time point analysis if applicable.

Safety and tolerability will be assessed by the incidence of treatment emergent-adverse events (TEAEs), physical examinations, vital signs measurements, changes in clinical laboratory parameters (including hematology, blood biochemistry, blood coagulation, and urinalysis), and 12-lead ECGs.

---

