**Part A:**

Approximately 70 subjects who are currently not being treated for their CHB infection will be randomized in a 3:1:3 ratio to receive one of the following treatments:

- Treatment Arm 1: JNJ-56136379 (N=30) (open-label)

After full recruitment, this treatment arm was discontinued early per Protocol Amendment 4. All subjects were to stop further dosing with JNJ-56136379 75 mg, start treatment with NA, and enter the post-treatment follow-up phase (Schedule 1).

- Treatment Arm 2: Placebo + NA (ETV or TDF) (N=10)
- Treatment Arm 3: JNJ-56136379 + NA (ETV or TDF) (N=30)

At the same time, approximately 40 subjects who are virologically suppressed by current NA treatment will be randomized in a 1:3 ratio to receive one of the following treatments:

- Treatment Arm 4: Placebo + NA (ETV or TDF) (N=10)
- Treatment Arm 5: JNJ-56136379 + NA (ETV or TDF) (N=30)

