## 6.1. Treatment Duration

All subjects will be treated for at least 24 weeks, unless they discontinue treatment early. Treatment will be extended for another 24 weeks in a treatment extension phase for subjects who meet the following criteria:

- Subject completed 24 weeks of treatment
- Subject had HBV DNA levels <200 IU/mL by Week 20 of the initial 24-week treatment period
- During the initial 24 weeks of treatment the subject did not have any safety concerns that would preclude continued treatment, as determined by the investigator
- For subjects who were enrolled in the study before the Amendment 2 came into effect: subject needs to consent for participation in the extension phase.

Subjects in the JNJ-56136379 250 mg monotherapy arm (Treatment Arm 6) who meet the treatment extension criteria, will receive JNJ-56136379 in combination with NA treatment from Week 24 to Week 48.

Subjects not meeting the above criteria will be followed-up until 24 weeks after EOT. These subjects should continue or, in case of JNJ-56136379 monotherapy, start NA treatment at the end of the 24-week study treatment as per local treatment guidelines.

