#### **Adverse Events**

The verbatim terms used in the eCRF by investigators to identify AEs will be coded using the Medical Dictionary for Regulatory Activities. Treatment-emergent AEs are AEs with onset during the treatment phase or that have worsened since baseline. For each AE (treatment-emergent and other), the percentage of subjects who experience at least 1 occurrence of the given event will be tabulated by study treatment. In addition, comparisons between treatment groups will be provided if appropriate.

Frequency tabulations, listings, datasets, or subject narratives may be provided, as appropriate, for those subjects who die, who discontinue treatment due to an AE, or who experience an AE of at least grade 2, at least possibly related, or an SAE.

For this study events of special interest (ESIs) are liver enzyme increases (eg, AST/ALT elevation). All ESIs will be listed in conjunction with other symptoms and laboratory abnormalities: eg, information on time of onset, duration of events, time to resolution, concomitant therapies, and relationship to study treatment.

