## **2.3. Definition of Analysis Phases, Periods, Types of Follow-up, Time Points and Visit Windows**

Analysis phase allocation will be included for all part of the analysis if applicable. The analysis periods and follow-up types will be presented in the efficacy part and the safety part (except for adverse events) of the analysis and in the general output if mentioned.

The analysis phase and periods and analysis time points are presented in the table 1 and table 2 below.

The procedures to be performed throughout the study at each time point are outlined in the time and events schedule in appendix 4, appendix 5 and appendix 6 of this document.

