**Table 1: Construction of phases**

Analysis phase	Analysis Period	Start date	End date
Screening (phase 1)		The date of signing the informed consent	1 day before the first study agent intake
Treatment (phase 2)	Initial Treatment	Date of first study agent intake	- If not included in the treatment extension°: Date of last study agent intake + 5 days*

Analysis phase	Analysis Period	Start date	End date
	(period 1)		- If included in the treatment extension o : Date of Week 24 study agent intake+5 days #
	Treatment Extension (period 2)	End of the initial treatment period + 1 day	Date of last study agent intake + 5 days*
Follow-up (phase 3)		End of the treatment phase +1 day	Trial termination date (date of last contact) or cut-off date for an interim analysis, whichever comes first

o depending on the answer in the FA dataset: FAOBJ = " WILL THE SUBJECT CONTINUE TREATMENT IN TREATMENT EXTENSION PHASE?" and whether actually treatment was extended in the EX dataset.

\* or study termination date (date of last contact) or cut-off date for an interim analysis, whichever comes first.

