### **Analyses:**

An overview table will show the number and percentage of subjects with at least one TEAE for several categories (e.g. AEs, serious AEs, and fatal AEs).

For each particular TEAE, the percentage and frequency of subjects who experience at least 1 occurrence of the given event will be tabulated. All adverse events will be sorted by incidence based on all subjects (column not provided). The following TEAEs tables will be included in the analysis:

- All TEAEs
- Serious TEAEs
- At least grade 3 TEAEs
- At least grade 2 TEAEs and related
- TEAEs leading to discontinuation
- Related TEAEs
- TEAEs in at least 2 subjects in total
- Events of special interest

All AEs, any serious TEAE, related TEAE, TEAE leading to death, TEAE leading to discontinuation, TEAE of at least grade 3, or ESI will be separately listed. Listings will include all information collected on the Adverse Event CRF pages (e.g. information on time of onset, duration of events, time of resolution, concomitant therapies and relationship to study treatment.)

---

For subjects reporting rash a listing with specific grade will be provided (see rash specific grade in **APPENDIX** ) and Rash Questionnaire will be tabulated by study treatment group and overall.

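### Adverse-event tables pool the initial 24 weeks with the extension and make no exposure adjustment, although treatment length differs between and within arms.

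*SAP*

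**What the plan says.** SAP 2.3 introduces analysis periods for the efficacy part and "the safety part (except for adverse events) of the analysis". SAP 6 repeats the exemption: AE displays are the ones "except for the adverse event displays which will be displayed by analysis phase and follow-up type". Because it appears twice, it reads as deliberate.

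SAP Table 1 makes the treatment phase a single phase containing two periods, initial treatment and treatment extension. For any subject it closes at "Date of last study agent intake + 5 days" (or earlier, at study termination or an interim cut-off). Under Analyses in SAP 6.1, for each TEAE "the percentage and frequency of subjects who experience at least 1 occurrence of the given event will be tabulated". No rate per person-time and no time-to-event analysis of AEs is planned. By contrast, the laboratory, ECG and vital-sign abnormality tables (SAP 6.2 to 6.4) are given per phase and period.

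On treatment length, Protocol 6.1 states: "Treatment will be extended for another 24 weeks in a treatment extension phase for subjects who meet the following criteria". The criteria are completing 24 weeks, HBV DNA below 200 IU/mL by Week 20, and no safety concern that precludes continuing; subjects enrolled before Amendment 2 must also consent. Arm 6 subjects who qualify continue 250 mg with NA added from Week 24 to Week 48. Of Arm 1, Protocol 3.1 says: "After full recruitment, this treatment arm was discontinued early per Protocol Amendment 4". Protocol 11.10 also foresees that "comparisons between treatment groups will be provided if appropriate".

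**The concern.** A percentage of subjects with at least one event grows with the time over which events are counted. If two columns of an AE table rest on different treatment times, they can differ with no difference in drug risk. Here the time depends on antiviral response (Week 20 HBV DNA), on tolerability (no precluding safety concern) and, in Arm 1, on a sponsor decision. None of these is balanced by randomisation.

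The second consequence concerns regimen. Protocol 2.1 asks for endpoints, safety included, to be evaluated by regimen, as monotherapy or coadministered. The SAP 2.6 layout has one 250 mg column and one 250 mg + NA column. SAP 2.1 assigns safety data by treatment arm, and no rule moves an Arm 6 subject's events after Week 24. Combination-period events would therefore sit in the monotherapy column.

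Safety is the first secondary objective listed. In a phase 2a trial, these tables are what a reader will use to compare doses and regimens.

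**Working it through.** **The plan's own durations.** Screening 8 weeks, treatment 24 or 48, follow-up 24 or 48 (Protocol 3.1): 8+24+24 = 56, 8+48+24 = 80 and 8+48+48 = 104 weeks. These match the participation times in Protocol 3.1 and confirm that 24- and 48-week subjects coexist by design. The documents state no AE risk, AE power or extension share.

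**Length of the AE window.** By SAP Table 1, without extension: 24×7 + 5 = 173 days. With extension: 48×7 + 5 = 341 days. The ratio is 341/173 = 1.97.

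**Effect on a crude percentage.** Assume a constant hazard, the same in every arm. Let p be the risk over a 173-day treatment phase and f the share of the arm that extends. Then

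crude % = (1−f)·p + f·[1 − (1−p)^(341/173)]

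For p = 30%, the 341-day risk is 1 − 0.7^1.97 = 50.5%. With f = 25%: 0.75×30 + 0.25×50.5 = 35.1%. Both p and f are assumptions, so a range is shown:

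| Assumed p | f = 0 | f = 25% | f = 50% | f = 75% | f = 100% |
|---|---|---|---|---|---|
| 10% | 10% | 12.2% | 14.4% | 16.6% | 18.8% |
| 30% | 30% | 35.1% | 40.2% | 45.4% | 50.5% |

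**Arm 6 attribution.** The extension adds 341 − 173 = 168 days. The share of Arm 6 treatment-phase time that falls in the extension on 250 mg + NA is 168f/(173 + 168f): 42/215 = 20% at f = 25%, 84/257 = 33% at f = 50%, and 168/341 = 49% at f = 100%.

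**Arm 1 exposure.** The stopping decision is dated 6 February 2019, and 168 days earlier is 22 August 2018. A subject first dosed before then, and still on treatment, had passed Week 24. Amendment 2, which introduced the extension, is dated 6 March 2018, about 48 weeks before the decision. Some Arm 1 exposure beyond 24 weeks was therefore possible, as was exposure well short of 24 weeks. No dosing dates are given to settle it.

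**Whether an initial-period table is enough.** For a subject stopped at an assumed 12 weeks, the window is 84 + 5 = 89 days and the risk is 1 − (1−p)^(89/173): 5.3% when p = 10% and 16.8% when p = 30%, against 10% and 30% for a 24-week subject. A table restricted to Weeks 0-24 would still mislead for Arm 1 subjects stopped early.

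**The case against.** The other side has a fair case.

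- The study is exploratory, with no formal testing, and Protocol 11.10 does not promise AE tables by period.
- The SAP tabulates exposure (4.6) and extension participation (4.1), and AE listings carry onset and duration.
- An unblinded Week 24 interim that includes safety may be run.
- Tables are also given by subject population. Suppressed subjects enter with HBV DNA below 60 IU/mL, so most should meet the HBV DNA criterion in both placebo + NA and combination arms. Tables for that population should be little affected.
- Arms are small. With 30 untreated subjects on a combination and 20 on pooled placebo + NA, a 40.2% versus 35.1% contrast (5.1 points) has a standard error of √(0.402×0.598/30 + 0.351×0.649/20) = 0.139, about 14 points. A modest artefact would be lost in noise.

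Much of this stands as mitigation, but none of it corrects the percentages. The exposure table is not split by subject population or HBeAg status, so it cannot be matched to the AE tables that are. The interim is optional, is triggered at 80% of subjects, and under staggered enrolment is not a clean Weeks 0-24 display.

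A reader might infer three stronger things that the documents do not support:

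- **That 24-week arms are set against 48-week arms.** No arm is defined that way. Arm 6 can run to Week 48, and Arm 1 subjects may have passed Week 24.
- **That AEs are the only safety display without a period split.** Physical examination is only listed (SAP 6.5).
- **That the best-suppressing arm must look less safe.** That needs a large gap in extension entry. The comparator is ETV or TDF, and Protocol 3.1 describes early HBV DNA declines on 75 mg monotherapy as similar to theirs, so nothing supports a particular gap.

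**Conclusion.** The point holds in a limited form. Followed as written, the SAP produces AE percentages over a treatment phase of about 173 or 341 days, with the mix set by response, tolerability and, in Arm 1, early closure. It also counts Arm 6 combination-period events as monotherapy events.

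The size and direction of any bias cannot be determined from the documents. Under equal, constant hazards, the apparent excess over an arm with no extension runs from about 2 points (p = 10%, f = 25%) to about 20 points (p = 30%, f = 100%). The top of that range requires every subject in one arm and none in the other to extend, which the documents do not suggest. If AEs cluster early, or if the tolerability criterion keeps event-prone subjects out of the extension, the excess would be smaller. This is a worthwhile, low-cost improvement to the safety analysis and does not affect the primary endpoint.

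**What to change.** 1. Remove the AE exception in SAP 2.3 and SAP 6.
2. Tabulate TEAEs for the initial 24-week period as the main between-arm display.
3. Show extension-period TEAEs separately and descriptively among subjects who entered it, with Arm 6 labelled 250 mg + NA. These subjects are selected on response and tolerability, so this is not a randomised comparison.
4. Add exposure-adjusted incidence for the initial period, which Arm 1 subjects stopped before Week 24 need, and for the whole treatment phase. State that a single rate assumes a roughly constant hazard.
5. State how Arm 6 events are attributed if the futility rule in Protocol 6.2 adds NA before Week 24, since a period split alone would not then separate the regimens.

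The cost is extra tables and programming. The allocation rules in SAP 6.1 are written for phases and must be extended to periods, including partial start dates and overlapping events that span Week 24. AE start dates and period dates are already collected or derived, so no new data are needed.

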## 6.1. Adverse Events

The verbatim terms used in the eCRF by investigators to identify adverse events (AEs) will be coded using the Medical Dictionary for Regulatory Activities (MedDRA version 20.1).

### **Allocation of adverse events into analysis phases:**

Adverse events are allocated to phases according to the start date (time). Treatment-emergent AEs (TEAE) are all AEs with a start date (no time) on or after the first administration of study agent or any ongoing event on the date of the first dose of study treatment that worsens in severity, intensity or frequency after the date of the first administration of study agent.

For the purpose of calculating treatment emergence and inclusion in summary tables, (incomplete) adverse event onset date will be allocated to a phase and overlapping AEs will be combined as below:

#### ***Step 1: allocation of events to the phases:***

Adverse events present in the SDTM database are allocated to phases based on their start date. If the start date of an event falls between (or on) the start and stop date of a phase, the AE is attributed to that phase (treatment-emergent principle). In case an AE has a start date and time, the date time of the first administration will also be taken into account.

Incomplete dates (i.e. time and/or day and/or month and/or year missing):

- In case of partial start or stop dates, the events are allocated to the phases using the available partial information on start and end date; no imputation will be done. If, for instance, for the AE start date only month and year are available, these data are compared to the month and year information of the phases. This rule may lead to multiplication of the event as a consequence of its assignment to multiple phases.

---

- In case of a completely missing start date, the event is allocated to the first active treatment phase, except if the end date of the AE falls before the start of the first active treatment phase.
- In case of a completely missing end date, the following decision rules apply:
  - in case the date is identified as unknown the date will remain missing
  - in case the date is not flagged as unknown the date is imputed by the cut-off date of the analysis for subjects still ongoing in the study, and by the end date of the last phase for subjects who discontinue.

Examples:

- Screening phase: start date: 02JAN2007 - stop date: 28JAN2007
- Treatment phase: start date: 29JAN2007 - stop date: 12AUG2007

1) Adverse event: start date: JAN2007- stop date: 15JUL2007

As the start date only has information about month and year, only this information will be used from the phases and therefore the AE will be assigned to the screening phase as well as to the treatment phase.

2) Adverse event: start date: JAN2007- stop date 27JAN2007

As the AE stops before or at the start of the treatment phase, it is only assigned to the Screening phase.

***Step 2: combination of events:***

Overlapping/consecutive events are defined as events of the same subject with the same preferred term who have at least 1 day in overlap or for which the start date of an event is 1 day after the end date of the preceding event. Overlapping/consecutive events may be combined into one AE or not, according to the following rules:

---

- In case a non-active phase (e.g. Screening) is followed by an active phase, and the overlapping/consecutive events start in both phases, they are allocated to their respective phase and are considered as separate events.
- In case overlapping/consecutive events start within a single phase, they are considered as one and the same AE. The individual events who contribute to this AE are retained as individual records in the Analysis Data Model (AdaM) database but are assigned the same onset, phase, and total duration.
- In case an active phase is followed by a non-active phase and the overlapping/consecutive events start in both phases, they are allocated to the active phase only and are considered as one and the same AE. The individual events who contribute to this AE are retained as individual records in the ADaM database but are assigned the same onset, treatment phase, and total duration.
- In case an active phase is followed by another active phase, and the overlapping/consecutive events start in both phases, they are allocated to their respective phase and are considered as separate AEs. The same rule applies for 2 non-active phases.

Remarks:

- Events can only be combined into one and the same AE if their start and stop dates are complete.
- In case the completely missing end date is imputed, this date is also considered as a complete date.
- Time is not considered when determining overlap of events.
- Adverse events will be reported from the informed consent date on (i.e. in screening phase until trial termination.

#### **Related AEs / Fatal AEs / events of special interest:**

AEs are defined as related or not related to the study agent or NA treatment. Related is defined as possible, probable, very likely relationship with the study agent or NA treatment, missing for the study agent. Not related is the categories not related and doubtful.

---

A subject has an AE leading to death if the outcome is defined as 'Fatal'. An AE leading to discontinuation is defined as an AE with 'Drug Withdrawn' as action taken in the dataset.

Events of special interest (ESIs) will be included in the analysis. These events indicated in the dataset with AECAT='SPECIAL INTEREST ADVERSE EVENTS'.

